10.0 EVALUATION DURING TREATMENT/INTERVENTION

10.1. General requirements

Evaluations during this period are per Table 10-1.

10.2. Treatment period

Patients will receive study treatments copanlisib and ibrutinib until disease progression, unacceptable toxicity or until other discontinuation criteria are met, whichever come first. Maximum duration of treatment is 36 cycles not exceeding 36 months.

Patients will follow the visit schedule as per Table 10-1. Permitted visit windows for assessments within the treatment period and at efficacy follow-up visits are included in the table. If copanlisib is held based on achievement of a complete response, patient visits will be every 2 cycles during C1-C6, every 3 cycles during C7-C12, every 4 cycles during C13-36.

Information on drug exposure will be collected on the Dosage Administration Record eCRF. Concomitant medications/significant non-drug therapies prior to start (\leq 28 days) and after start of study treatment will be recorded on the appropriate eCRFs.

Compliance will be assessed by the investigator and/or study personnel at each visit using box counts and information provided by the caregiver.

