10.3. End of treatment visit including premature withdrawal and study safety followup

Patients will continue study treatment until disease progression, until any of the study's discontinuation criteria are met, or a maximum treatment period of 36 cycles, not exceeding 36 months (Section 13). Patients who discontinue study treatment or at completion therapy should be scheduled for an End-of-Treatment visit within 7 days from treatment discontinuation or as early as possible per patient's convenience at which time all of the assessments listed for the EOT visit will be performed. For details of assessments, refer to Table 10-1. An End of Treatment eCRF page should be completed, giving the date and reason for discontinuation of study treatment. Patients will have an additional follow up 1 month after last dose.

If a patient withdrawal occurs, or if the patient fails to return for visits, the investigator must determine the primary reason for a patient's premature withdrawal from the study and record this information on the End of Treatment eCRF page.

Patients will be assessed for any adverse events 30 days, \pm 7 days, from the last dose of either study drug or until new therapy is initiated, whichever comes first.

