T3, T4, TSH		X				As clinically indicated			X
Fructosamine		X			X	X			X
Hemoglobin A1c		X				X			X
Coagulation (PT/PTT)		X							X
B cell Clonality by NGS			X			Day 1 Cycle 3, 5, 7, 10, 13, 17, 21, 25, 29, 33			X
Hepatitis B/C ^B	X					Hepatotoxicity testing/procedures as clinically indicated ^C			
HIV	X								
Cytomegalovirus PCR	X					X			X
Serum/Urine beta-HCG for women of childbearing age		X							
Post Infusion Glucose Evaluation ^D			X ^D Fasting	X ^D	X ^D	X ^D	X ^D		
Post Infusion Blood Pressure ^E			X ^E	X ^E	X ^E	X ^E	X ^E		
Radiographic assessment ^F	X					Before Day 1 Cycle 3, 5, 7 (first 6 months), 10, 13, (1 year), 17, 21, 25, 31 (year 2-3)		X (if not within 4 weeks)	
ECHO or MUGA	X							X	
ECG	X							X	

PCP pneumonia prophylaxis			Continuous (unless clinically contraindicated)				
Pill Diary			X		X		X
Tumor biopsy(archived/fresh biopsy) ^G	X ^G				Optional ^G		
Research Blood Tests: ctDNA, ctRNA		X	X	X	Cycle 2: D1, D8, D15 Cycle 3-7: D1	X	
Research Blood Tests: Pharmacokinetics ^J				X			

A: Copanlisib Dosing: If copanlisib is held based on achievement of a complete response, patient visits will be every 2 cycles during C1-C6, every 3 cycles during C7-C12, every 4 cycles during C13-36.
B: Hepatitis Evaluation: HbsAg, HBcAb, anti-HCV Ab, Hep B/C PCR if positive
C: Additional viral hepatitis workup as clinically warranted: HAAb, HBsAg, HBsAb, HBcAb, HCV RNA or HDV RNA (where needed), H EAb, CMVAb, EBcAb, CMV IgM Ab, EBV IgM Ab, HSV, AP, CPK, LDH, Carriers of hepatitis B should be closely monitored for clinical and laboratory signs of active HBV infection, signs of hepatitis during and for several months following ibrutinib/copanlisib treatment. Carriers of hepatitis B (positive HBsAg and/or HBcAg but negative HBV-DNA is required to be on prophylactic antiviral therapy. If viral load becomes positive, patients should be withdrawn from study. Hep C carriers (anti-HCV Ab positive, negative HCV-RNA PCR must be tested monthly for HCV reactivation. If HCV-RNA PCR becomes positive, patients should be withdrawn from study.
D: Post Infusion Glucose Evaluation: C1D1 – fasting glucose prior to copanlisib (0h), 60 min (end of infusion) and 2 hours; all subsequent doses – non-fasting glucose prior to copanlisib (0h), post infusion.

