E: Post Infusion Blood Pressure Evaluation: Blood pressure (5-10min, +/- 10 min) prior to copanlisib must be <150/90mmHg for two consecutive measurements. If blood pressure prior to infusion is ≥150/90 mmHg, medical intervention or dose delay should be considered. Blood pressure post infusion should be measured at 30 min (mid-infusion), 60 min (end of infusion), 1 hour and 2 hour post infusion (+/- 10 min).
F: Radiographic assessment via PET and CT chest/abdomen/pelvis and neck CT if clinically indicated (MRI will be used for those who are unable to undergo CT scans).
G: Pretreatment archived biopsy material (10-15 x 10 microns) or an optional pretreatment core biopsy (2-3 cores). Post treatment optional core biopsy (2-3 cores).
H: Maximum 36 cycles, not exceeding 36 months of treatment
J: Exact schedule for PK testing is in Table 9-4.
K: Not required to collect if patient has begun new anti-cancer therapy within 30 days after last dose of either study drug on protocol.

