12.0 CRITERIA FOR THERAPEUTIC RESPONSE/OUTCOME ASSESSMENT

Response and progression of disease will be evaluated in this study using the RECIL criteria[37]. Clinical evaluation and tumor assessments will be performed periodically, as is indicated in Table 10-1, based on physical examination, radiological evaluation and core bone marrow biopsy (in patients

with pre-existing bone marrow involvement). Clinical suspicion of disease progression at any time will require a physical examination and radiological confirmation to be performed promptly, rather than waiting for the next scheduled tumor assessment. In case of an unscheduled or delayed tumor assessment for any reason, subsequent tumor assessments must be performed according to the originally planned schedule from baseline.

Measurability of lesion for objective response and measurement of target lesions: Measurable disease: lesions that can be accurately measured in two dimensions by CT, MRI, plain x-ray or other conventional technique and have a greatest transverse diameter of 1.5 cm or greater. Non-measurable disease: All other lesions including uni dimensional lesions, lesions too small to be considered measurable, pleural or pericardial effusions, ascites, bone disease, leptomeningeal disease, lymphangitis, pulmonitis, abdominal masses not confirmed by CT, or disease documented only by indirect evidence (e.g. lab values).

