14.2. Phase II

The primary objective for this phase II cohort is to assess the complete response rate based on best response by 6 months of ibrutinib and copanlisib and the secondary objective is to measure the disease control rate (stable disease, partial response, and complete response), overall response rate (partial and complete response), duration of response, progression and event free survival. A Simon mini-max two stage design will be used with the goal to increase by complete response rate based on best response by 6 months from 20% to 40%. In first stage, if 5 or more of 18 patients have responses, then the trial will proceed to stage 2. In stage 2, additional patients are enrolled to make the total sample size 33. If 11 or more responses are observed, then the combination is deemed promising. Accrual will not be held while the initial 18 patients in the first stage are evaluated for the 6-month response endpoint. The one sided type I error rate is 0.05 and the power is 0.80. A total of 33 patients will be enrolled, though patients treated at MTD/RP2D from phase I portion of the study will be included in the phase II analysis. Expected accrual is 2-3 patients per month and so the phase II portion will be completed within a year.

For other secondary objectives, the event free survival and progression free survival rates will be assessed by the Kaplan-Meier estimation. Event free survival is defined from the date of first dose to progression, or death, and any events including treatment discontinuation for adverse events or severe adverse events whichever came first. Progression free survival is defined from the date of first dose to progression or death, whichever came first. The duration of response will also be assessed by Kaplan-Meier method but on a sub-cohort of patients who showed any response.

To protect patients from excessive toxicity of the treatment during the entire treatment period, several stopping rules are implemented during the study based on the maximum total number of treated patients in both phase I and II (45). **Treatment related Grade ≥ 3 Pneumonitis or Colitis:** 10% unacceptable rate, 2.5% acceptable rate. Trial to hold enrollment if ≥ 4 deaths related to treatment at any point during the study. Otherwise, hold enrollment based on number of treated patients.

Number of treated patients	1	14	33	45
Number of Gr ≥ 3 Pneumonitis/Colitis to stop the trial	1	2	3	4

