14.3 Treatment re-initiation

Patients who discontinue copanlisib may restart if they meet requirements set out in Section 9.9 and after discussion with study PI. Patients who have a complete response, then restart copanlisib for progression will be counted as a progression. Future responses will be censored.

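### Section 10.2 refers to efficacy follow-up visits that Table 10-1 does not contain, so patients who stop treatment without progression have no later scheduled progression or survival assessment

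*Combined protocol and SAP*

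**What the plan says.** Section 10.2 says of Table 10-1: "Permitted visit windows for assessments within the treatment period and at efficacy follow-up visits are included in the table".

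The radiographic row of Table 10-1 reads "Before Day 1 Cycle 3, 5, 7 (first 6 months), 10, 13, (1 year), 17, 21, 25, 31 (year 2-3", with a further scan at EOT if none was done in the preceding 4 weeks. After EOT the table has one column, the 30-day follow-up, and its radiographic cell is empty. Section 10.3, whose title presents this as safety follow-up, says "Patients will have an additional follow up 1 month after last dose" and ties the contact to adverse events. Section 9.7 refers patients who stop for an adverse event back to Section 10.

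No row of the table records the start of new anti-lymphoma therapy. Footnote K says of concomitant medications: "Not required to collect if patient has begun new anti-cancer therapy within 30 days after last dose of either study drug on protocol".

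On the analysis side, Section 14.2 states "Progression free survival is defined from the date of first dose to progression or death, whichever came first" and "The duration of response will also be assessed by Kaplan-Meier method but on a sub-cohort of patients who showed any response". It gives no censoring rule for either endpoint and no start date for DOR. Section 14.3 counts a copanlisib restart for progression after complete response as a progression, then adds "Future responses will be censored". Section 14.4 plans Kaplan-Meier and Cox analyses of OS.

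**The concern.** The plan foresees several ways of stopping without progression: toxicity (Table 9-7), withdrawal (Section 13) and completing 36 cycles (Section 4.3). PFS, DOR and OS all need information from these patients after they stop. Followed as written, the schedule collects none beyond 30 days.

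Two things are at stake. The PFS and DOR curves could lose events and precision. And if the analyst censors at the last on-treatment scan, the censoring could be informative, because patients who stop for toxicity or by choice may progress sooner or later than those who continue. With no stated rule, two analysts could follow the plan and report different PFS and DOR from the same patients. Table 9-7 and its notes also take some patients off study, and Section 13 withdraws patients from the study, without saying whether outcome follow-up continues.

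**Working it through.** **1. The passages side by side.** Section 4.3 defines a cycle as 28 days of therapy, so cycle-based scans end when therapy ends. What remains is the EOT scan and the 30-day contact. Section 10.3 independently describes the same two contacts, so the missing visit is not an artefact of how the table was read. The efficacy follow-up visits named in Section 10.2 appear nowhere else in Section 10.

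**2. What the plan's own figures cover.** Section 14.2 gives figures only for the response endpoint: at least 5 of 18, then at least 11 of 33, for 20% against 40%, one-sided alpha 0.05 and power 0.80. The exact two-stage sum over x = 5 to 18 of P(Bin(18,p) = x) × P(Bin(15,p) ≥ 11 − x) gives 0.0458 at p = 0.20 and 0.801 at p = 0.40. The stated design reproduces, and the gap does not touch it.

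**3. Illustration of lost events.** The documents give no stopping rate and no follow-up horizon, so these are assumptions:
- PFS: n = 33, exponential, median 13.9 months. DOR: n = 22 (68% of 33), median 17.5 months. The medians and the 68% are the ibrutinib-alone figures in Section 3.0, used as stand-ins.
- A proportion d = 15%, 25% or 35% per year stop without progression.
- The hazard is unchanged after stopping, and every later event is missed.

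With λ = ln 2 / median and g = −ln(1 − d)/12:
- all events by T = n(1 − exp(−λT))
- captured events = n · λ/(λ+g) · (1 − exp(−(λ+g)T))

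For PFS, λ = 0.0499 per month and g = 0.0135, 0.0240 or 0.0359.

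| Endpoint, T | All events | Captured (15/25/35%) | Lost | Lost if half recovered |
|---|---|---|---|---|
| PFS, 24 months | 23.0 | 20.3 / 18.5 / 16.7 | 12 / 20 / 27% | 6 / 10 / 14% |
| PFS, 36 months | 27.5 | 23.3 / 20.7 / 18.3 | 15 / 25 / 33% | 8 / 12 / 17% |
| DOR, 24 months from response | 13.5 | 11.8 / 10.7 / 9.7 | 12 / 21 / 28% | – |
| DOR, 36 months from response | 16.7 | 14.0 / 12.3 / 10.8 | 16 / 26 / 36% | – |

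The percentages do not depend on n. This matters because the secondary objectives cover both phases, with up to 45 treated patients.

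In precision terms, the log-scale interval for PFS widens by √(all/captured) − 1. That is 6-17% at 24 months (for example √(23.0/16.7) = 1.17) and 9-23% at 36 months.

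**4. Illustration of bias.** Suppose the analysis censors at stopping and the hazard afterwards is HR × λ. The Kaplan-Meier curve then targets exp(−λt), median 13.9 months. The true curve is

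S(t) = exp(−(λ+g)t) + g[exp(−HR·λt) − exp(−(λ+g)t)]/(λ + g − HR·λ).

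| Hazard after stopping | True median (15/25/35%) | Error in the reported 13.9 |
|---|---|---|
| halved | 14.7 / 15.3 / 16.0 | 0.8 to 2.1 months too low |
| unchanged | 13.9 | none |
| 1.5-fold | 13.4 / 13.1 / 12.7 | 0.5 to 1.2 months too high |
| 3-fold | 12.5 / 11.7 / 11.0 | 1.4 to 2.9 months too high |

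For comparison, an approximate 95% interval around 13.9 months with 18.5 events is 13.9 × exp(±1.96/√18.5) = 8.8 to 21.9 months.

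**The case against.** The plan is not silent about events after treatment. Section 12 says "Clinical suspicion of disease progression at any time will require a physical examination and radiological confirmation to be performed promptly", and Section 17.1 requires the date and cause of death of every patient entered. Section 14.3 supplies an event rule for patients who restart copanlisib after complete response. Section 13 makes starting another anti-neoplastic therapy a reason to stop, and the EOT form records that reason and its date, so new therapy is missed only when it begins later. Section 9.7 and the notes to Table 9-7 let patients who are clearly benefiting stay on treatment in exceptional situations, and complete responders whose copanlisib is held continue ibrutinib; both groups stay on the scan schedule.

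All of this stands and narrows the exposed group. It does not close the gap. None of these provisions supplies a contact through which the site would learn of a progression or a late new therapy, and none says how a patient who stops without progression is handled in the analysis.

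A reader might infer more than the documents support:
- *That PFS and DOR will be biased, or will certainly lose events.* No stopping rate is given, bias needs a hazard that changes after stopping, and its direction is unknown.
- *That the protocol censors at EOT.* It states no rule; that is only one possible handling.
- *That the trial's decision is compromised.* Complete response by 6 months and the Simon rule do not use post-treatment follow-up, and no decision rule is attached to PFS or DOR.

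**Conclusion.** The mismatch between Section 10.2 and Table 10-1 is plain on the text, and it has a practical result: patients who stop without progression have no systematic follow-up for endpoints that the plan intends to estimate. PFS and DOR could lose events and could carry informative censoring of unknown direction. EFS counts stopping for an adverse event but is exposed for other stops, such as withdrawal or completing 36 cycles. OS in Section 14.4 has no scheduled source of vital status beyond the duty to report deaths.

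The size is moderate and rests wholly on the assumed stopping rates and the borrowed medians. Not all of the loss is avoidable, since withdrawal of consent and loss to follow-up would remain. The undefined DOR dates and the handling of new therapy would on their own be missing detail; they matter here because no follow-up stands behind them. The sponsor should correct this, but it does not threaten the primary analysis.

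**What to change.** **Preferred.** Add a post-treatment row to Table 10-1 for patients who stop without progression. By chart review or telephone at a fixed interval (for example about every 3 months), record progression from standard-of-care imaging with scan dates, start of new anti-lymphoma therapy, and vital status. Continue until progression, death, withdrawal of consent or study close, with vital status continuing after progression for OS. State that coming off treatment, including where Table 9-7 or Section 13 takes a patient off study, does not end this follow-up unless consent is withdrawn.

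In Section 14.2, state that PFS and DOR use these dates and are not censored at treatment discontinuation, and define when DOR starts and ends. Pre-specify one handling of new therapy before progression (counting later progression or death, or censoring at the last tumour assessment before new therapy), with the other as a sensitivity analysis.

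**Minimum.** If follow-up will not be added, delete the reference to efficacy follow-up visits, state the censoring rule, and report PFS, DOR and OS as limited by on-treatment follow-up.

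**Cost.** The preferred option needs one follow-up form and modest abstraction for at most 45 patients at a single institution, with no added protocol scans. Its downsides are that off-treatment scan dates are less regular, so later progression dates are less precise, and that patients who withdraw consent or are lost are still not recovered. The minimum option costs only text.

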10.3. End of treatment visit including premature withdrawal and study safety followup

Patients will continue study treatment until disease progression, until any of the study's discontinuation criteria are met, or a maximum treatment period of 36 cycles, not exceeding 36 months (Section 13). Patients who discontinue study treatment or at completion therapy should be scheduled for an End-of-Treatment visit within 7 days from treatment discontinuation or as early as possible per patient's convenience at which time all of the assessments listed for the EOT visit will be performed. For details of assessments, refer to Table 10-1. An End of Treatment eCRF page should be completed, giving the date and reason for discontinuation of study treatment. Patients will have an additional follow up 1 month after last dose.

If a patient withdrawal occurs, or if the patient fails to return for visits, the investigator must determine the primary reason for a patient's premature withdrawal from the study and record this information on the End of Treatment eCRF page.

Patients will be assessed for any adverse events 30 days, \pm 7 days, from the last dose of either study drug or until new therapy is initiated, whichever comes first.

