10.4. Correlative studies

Patients consented on this trial will have tumor samples analyzed for genomic alterations via next generation targeted sequencing. Optional post treatment biopsy will be obtained to compare the differences in genomic alterations prior to treatment and post treatment. In addition, circulating tumor DNA and circulating tumor RNA samples will be collected throughout treatment to serially assess the genomic profile of treated patients.

Gene sequencing will be performed in the CLIA certified Molecular Diagnostics Service laboratory, a division of the MSKCC Pathology Department, using IMPACT-Heme (Integrated Mutation Profiling for Actionable Cancer Targets Hematology Panel) with paired tumor and normal tissue samples, or a custom panel of genes depending on baseline IMPACT-Heme results. IMPACT provides full exon coverage of 410 cancer related genes including CARD11, MYD88, PIK3CA, BTK, and can be used to detect base substitutions, small indels, copy number alterations and select gene re-arrangements. In some cases, the Molecular Diagnostic Service will utilize an additional assay, such as Sanger Sequencing, B cell clonality, or fluorescence in situ hybridization (FISH), to confirm specific results from these multiplexed assays. We will assess for the following:

- 1) Determine variations on circulating tumor RNA throughout treatment
- 2) Correlate spectrum of genomic mutations in tumor tissue versus circulating tumor DNA
- 3) Assess tumor variant allele frequency in circulating tumor DNA
- 4) Correlate circulating tumor DNA to radiographic response

Table 10-1. Schedule of Evaluation

Timepoint	Screening	C1D1	C1D8	C1D15	CxD1	CxD8	CxD15	EOT	30 day FU after last dose ^H
Window	-28	-7		+/- 3 days	+/- 3 days	+/-3 days	+/-3 days	+/- 7 days	+/- 7 days
Treatment									
Copanlisib		X	X	X	X ^A	X ^A	X ^A		
Ibrutinib					Daily				
Evaluation									
Obtain Informed Consent	X								
Demography	X								
Inclusion/Exclusion criteria	X								
Medical/Diagnosis/Treatment history	X								
Prior/Concomitant medications	X		X	X	X				X ^K
Physical Examination	X		X	X	X			X	X
ECOG and Vitals (Weight, Blood pressure, Pulse, Resp, Temp)	X		X	X	X			X	
Hematology: CBC with Diff		X	X	X	X	X		X	
Chemistry(BMP, TBili, AST, ALT, TP, Alb, AP, UA, LDH, amylase, lipase, GFR, Mag, Phos)		X	X Fasting	X	X	X	X	X	
Lipid panel		X				Day 1 Cycle 3, 5, 7, 10, 13, 17, 21, 25, 29, 33			X
Urinalysis, Urine protein						As clinically indicated			X

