11.0 TOXICITIES/SIDE EFFECTS

11.1. Adverse Event

11.1.1. Definitions and reporting

An adverse event is defined as the appearance of (or worsening of any pre-existing) undesirable sign(s), symptom(s), or medical condition(s) that occur after patient's signed informed consent has been obtained. Abnormal laboratory values or test results occurring after informed consent constitute adverse events only if they induce clinical signs or symptoms, are considered clinically significant, require therapy (e.g. hematologic abnormality that requires transfusion or hematological stem cell support), or require changes in study medication(s).

Adverse events that begin or worsen after informed consent should be recorded in Medidata. Conditions that were already present at the time of informed consent should be recorded in the Medical History in Medidata. Adverse event monitoring should be continued for at least 30 days following the last dose of study treatment or until initiation of new therapy, whichever comes first. Adverse events (including lab abnormalities that constitute AEs) should be described using a diagnosis whenever possible, rather than individual underlying signs and symptoms. When a clear diagnosis cannot be identified, each sign or symptom should be reported as a separate Adverse Event.

Adverse events will be assessed according to the Common Terminology Criteria for Adverse Events (CTCAE) version 5.0. If CTCAE grading does not exist for an adverse event, the severity of mild, moderate, severe, and life-threatening, corresponding to Grades 1 - 4, will be used. CTCAE Grade 5 (death) will not be used in this study; rather, information about deaths will be collected through a Death form.

The occurrence of adverse events should be sought by non-directive questioning of the patient (subject) during the screening process after signing informed consent and at each visit during the study. Adverse events also may be detected when they are volunteered by the patient (subject) during the screening process or between visits, or through physical examination, laboratory test, or other assessments. As far as possible, each adverse event should be evaluated to determine:

- The severity grade (CTCAE Grade 1-4)
- Its duration (Start and end dates)

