17.3 Serious Adverse Event (SAE) Reporting

An adverse event is considered serious if it results in ANY of the following outcomes:

- Death
- A life-threatening adverse event
- Development of a new malignancy
- Pregnancy
- An adverse event that results in inpatient hospitalization or prolongation of existing hospitalization
- A persistent or significant incapacity or substantial disruption of the ability to conduct normal life functions
- A congenital anomaly/birth defect
- Important Medical Events (IME) that may not result in death, be life threatening, or require hospitalization may be considered serious when, based upon medical judgment, they may jeopardize the patient or subject and may require medical or surgical intervention to prevent one of the outcomes listed in this definition

Note: Hospital admission for a planned procedure/disease treatment is not considered an SAE.

SAE reporting is required as soon as the participant starts investigational treatment/intervention. SAE reporting is required for 30-days after the participant's last investigational treatment/intervention. Any event that occurs after the 30-day period that is unexpected and at least possibly related to protocol treatment must be reported.

Please note: Any SAE that occurs prior to the start of investigational treatment/intervention and is related to a screening test or procedure (i.e., a screening biopsy) must be reported.

All SAEs must be submitted in PIMS. If an SAE requires submission to the HRPP office per IRB SOP RR-408 'Reporting of Serious Adverse Events', the SAE report must be submitted within 5 calendar days of the event. All other SAEs must be submitted within 30 calendar days of the event.

The report should contain the following information:

- The date the adverse event occurred
- The adverse event
- The grade of the event
- Relationship of the adverse event to the treatment(s)
- If the AE was expected
- Detailed text that includes the following
 - An explanation of how the AE was handled
 - A description of the participant's condition
 - Indication if the participant remains on the study
- If an amendment will need to be made to the protocol and/or consent form • If the SAE is an Unanticipated Problem

For IND/IDE protocols:

The SAE report should be completed as per above instructions. If appropriate, the report will be forwarded to the FDA by the IND Office

17.2.1

Bayer specific SAE reporting:

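### The final safety assessment may fall as early as Day 23 after the last dose, leaving up to 7 of the 30 required days without any scheduled adverse event ascertainment

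*Combined protocol and SAP*

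**What the plan says.** Three parts of the document govern safety follow-up after the last dose.

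- **Timing of the assessment.** Section 10.3 sets the adverse event assessment at "30 days, \pm 7 days, from the last dose of either study drug", with the cut-off "or until new therapy is initiated, whichever comes first". It also states: "Patients will have an additional follow up 1 month after last dose". In Table 10-1 the last column is the "30 day FU after last dose", with a window of ± 7 days.
- **Length of adverse event monitoring.** Section 11.1.1 states: "Adverse event monitoring should be continued for at least 30 days following the last dose of study treatment", again with an earlier end at new therapy ("or until initiation of new therapy, whichever comes first").
- **Length of SAE reporting.** Section 17.3 states: "SAE reporting is required for 30-days after the participant's last investigational treatment/intervention". That sentence has no exception for new therapy. After the 30 days, only unexpected events that are at least possibly related remain reportable under 17.3.

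Section 9.8 also asks that new malignancies be collected for 30 days after treatment.

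**The concern.** A symmetric window is harmless when the nominal day is only a target. Here Section 11.1.1 makes Day 30 a floor, and Section 17.3 makes it the end of a period that must be covered. The lower half of the window therefore permits a final visit that cannot establish what happened in the remaining required days. Such a visit follows Section 10.3 and Table 10-1, so it would not be flagged as a deviation and nothing would prompt the site to contact the patient again.

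At stake is how complete, and how comparable between patients, the post-treatment adverse event data are. Two patients with the same experience after stopping could contribute different records only because one was seen on Day 24 and the other on Day 34.

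**Working it through.** The plan states no figure for this gap, so there is nothing to reproduce. The check is window arithmetic plus a search for any later contact.

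**Inputs.** Nominal day 30 and window ± 7 days (Section 10.3; Table 10-1, last column). Required coverage 30 days (Sections 11.1.1 and 17.3).

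**Step 1: permitted visit days.** Earliest = 30 − 7 = Day 23. Latest = 30 + 7 = Day 37.

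**Step 2: days left without scheduled ascertainment.** For a visit on day v, the gap is max(0, 30 − v).

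| Visit day | Days not covered | Share of 30 days |
|---|---|---|
| 23 | 7 (Days 24 to 30) | 7/30 = 23% |
| 26 | 4 | 4/30 = 13% |
| 29 | 1 | 1/30 = 3% |
| 30 to 37 | 0 | 0% |

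**Step 3: an illustrative average.** The documents give no distribution of visit days. If visits were spread evenly over the window (an assumption):

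- in whole days, 7 of the 15 permitted days (23 to 37) precede Day 30, so 7/15 = 47% of patients would be seen early. The mean gap over all patients would be (7+6+5+4+3+2+1)/15 = 28/15 = 1.87 days, or 6.2% of 30;
- on a continuous scale, half would be seen early, with a mean gap of (7²/2)/14 = 24.5/14 = 1.75 days, or 5.8% of 30.

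The possible range is from 0 days, if every visit is on or after Day 30, to 7 days, if every visit is on Day 23.

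**Step 4: is there a later scheduled contact?** Table 10-1 has no column after the 30-day follow-up. Section 10.3 adds only the one-month visit already counted. Section 10.2 refers to efficacy follow-up visits, but the table schedules none after that column. Section 11.1.1 follows events to resolution once they are detected, which does not detect a new event on Days 24 to 30.

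**Step 5: what is caught without a visit?** Section 17.1 requires any death, whatever its cause, to be reported and makes the treating physician responsible for its date and cause. Section 17.2.1 requires every SAE after the start of copanlisib to go to the manufacturer within 24 hours, with no stated end date. Section 17.3 continues to require SAEs through Day 30. Section 11.1.1 accepts events volunteered between visits. The gap therefore bears mainly on non-fatal events that nobody volunteers.

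**Step 6: new therapy.** Sections 10.3 and 11.1.1 both stop at the start of new therapy, while the 30-day sentence in Section 17.3 does not. For a patient who starts new therapy before Day 30, the SAE period outlasts the scheduled assessment.

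**The case against.** The strongest reply is that a visit window is not a monitoring period. Sections 10.3 and Table 10-1 time one assessment; Sections 11.1.1 and 17.3 set how long the duty lasts. A site can satisfy all of them: a visit on Day 25 is in window, and an event on Day 28 is still reportable. This stands. A reader might infer that collection closes at Day 23, but no passage says so.

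A reader might also infer that late deaths, or severe events such as pneumonitis, are under-counted and that the Section 14.2 stopping rules are distorted, because the pneumonitis/colitis and death boundaries turn on few events (2 at 14 patients, 3 at 33, 4 at 45). The documents do not support that. Deaths have a route that depends on no visit, and events meeting the SAE definition have theirs. Section 14.2 describes the rules as protecting patients over the whole treatment period and never mentions the follow-up visit. Its wording about any point during the study is attached to the maximum counts and does not define a post-treatment window. No change in a count or a stopping probability has been demonstrated.

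A third reply is that the minimum is not absolute, because new therapy can end adverse event monitoring early, and that moving the window to + 7 days would remove the early slot in which such patients can now be seen. This too stands, and the remedy has to provide for it.

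What the reply does not remove is that the schedule accepts a final contact before the stated minimum has elapsed and relies on spontaneous reporting for the rest.

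**Conclusion.** The passages do not agree, and the effect is small. A patient seen on Days 23 to 29 has 1 to 7 of the 30 required days (3% to 23%) without scheduled ascertainment and with no later visit in Table 10-1. The likely loss is confined to new, non-fatal, unvolunteered adverse events in those days. The primary endpoint, the sample size and the cycle 1 DLT assessment are untouched.

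The maximum of 7 days follows from the documents alone. The average of about 1.8 days rests on an even spread of visits, which is only illustrative. Both count days from a single last dose; Section 10.3 does not say which drug's last dose applies when the two stop at different times.

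**What to change.** Reconcile Sections 10.3, 11.1.1 and 17.3 and Table 10-1 in one of two ways:

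1. change the follow-up window in Section 10.3 and Table 10-1 to 30 days + 7 days (Days 30 to 37); or
2. keep ± 7 days and require an adverse event and SAE status contact on or after Day 30 for anyone seen earlier. A telephone call is enough.

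Under either option, keep the new-therapy cut-off and add that, when new therapy starts before Day 30, the adverse event assessment is done before it starts and SAE status is still collected through Day 30, as Section 17.3 requires.

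The change affects data collection only. It costs an edit to the window in two places or one added sentence, plus slightly less scheduling freedom under the first option or one extra call for some patients under the second.
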